4.3. Enrollment Target and Study Duration

Approximately 67 subjects will be enrolled in the study with a minimum of 56 subjects targeted to complete the study. The point of study enrollment is defined as the execution of the informed consent and assent at Visit 1.

Approximately 4 – 6 clinical sites in the United States will participate in the study. Each site is expected to screen (enroll) up to 17 subjects with a minimum 10 subjects completing the study. Subjects will be enrolled among participating clinical sites to ensure the target number of completed subjects is met.

The total duration of the study enrollment will be approximately 10 weeks, unless otherwise approved by the Sponsor.

Clinical Study Protocol

Johnson & Johnson Vision Care, Inc.

There will be one scheduled visit in this study. Eligible subjects will be bilaterally fitted with both test articles within one visit. The total duration of the study is expected to be 12 weeks (including the enrollment period).

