14.2. Sample Size Justification

This study was designed and powered to demonstrate non-inferiority of the Test lens (EMO-200) compared to the Control lens (EMO-118) with respect to monocular distance logMAR visual acuity under bright HLHC and lens fit acceptance after 10-minute lens settling period. The ample size was calculated for both the primary and secondary endpoints to achieve a minimum statistical power of 80% using a 2-sided type I error of $\alpha=0.05$ based on historical data from [REDACTED] [REDACTED] was a 2×2 crossover study with two study lenses (EMO-116 and EMO-118). In [REDACTED] all eyes had acceptable lens fit. Table 6 below presents the descriptive statistics of monocular logMAR visual acuity under bright HLHC at fitting observed from [REDACTED].

Clinical Study Protocol

Johnson & Johnson Vision Care, Inc.

Table 6: Descriptive Summary of Monocular LogMAR Visual Acuity Post Lens-Fitting from [REDACTED] – Per Protocol Subjects

	EMO-116	EMO-118
Number of eyes	50	50
Mean (SD)	-0.03 (0.098)	0.01 (0.082)

SD = standard deviation

Monocular Distance logMAR Visual Acuity

The sample size estimate for monocular distance logMAR visual acuity was calculated using a linear mixed model-based power analysis method³³. The model included lens, period, and lens wear sequence as fixed effects. An unstructured (UN) covariance matrix was used to model the residual errors between measurements within the same subject and eye across study periods. It was assumed there was no difference between the Test and Control lenses since the two study lenses have not been evaluated in the same study previously. Sample size estimation was carried out using an approximation of the power of an F-test derived from the non-centrality parameter calculated from the observed F statistic of the linear mixed model. Below is the variance-covariance matrix used in the sample size calculation for monocular logMAR visual acuity.

Subject intercept: 0.003087

The UN covariance matrix:
$$\begin{bmatrix} 0.004953 & -0.00076 \\ -0.00076 & 0.005157 \end{bmatrix}$$

Lens Fit Acceptance

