Acceptable lens fit is a binary response as $Y = 1$ if a subject eye has an acceptable fit and $Y = 0$ otherwise. Indicated by the historical data from [REDACTED] there was no unacceptable lens fitting for both study lenses. Assuming no difference between study lenses and a correlation of 0.80 between left and right eyes within the same subject and period; and a correlation of 0.50 between measurements within the same subject across periods, a total of 2000 replicating trials were simulated with a reference (Control lens) rate of 95% (worse-case scenario) for lens fit acceptance. Given the rare event binary outcome of fit acceptance (i.e., the number of unacceptable fit is very small), each replicated sample was analyzed using a Bayesian beta-binomial model with correlated binary data (Diniza et al; 2010).³⁴ Sample size was estimated to achieve a minimal statistical power of 80% with a non-inferiority margin of -10% (Test – Control). Table 7 summarizes the required number of subjects for each of the primary and secondary endpoints to achieve a minimum of 80% statistical power with a 2-sided type I error of 0.05.

Table 7: Sample Size and Power for the Primary and Secondary Endpoints

Endpoints	Test/Margin	Sample size	Power
Monocular LogMAR VA	Non-inferiority (0.05)	28	92%

Clinical Study Protocol

Johnson & Johnson Vision Care, Inc.

Lens Fit Acceptance	Non-inferiority (-10%)	56	81%
---------------------	------------------------	----	-----

As indicated in Table 7 above, the sample size chosen for this study was primarily driven by lens fit acceptance in order to achieve a statistical power of at least 80% for both primary and secondary endpoints. The plan is to enroll approximately 67 subjects with a target of 56 to complete the study.

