It is assumed that β_0 , β_1 and ρ to be independent with a non-informative prior $N(0, 1000)$ for β_0 and β_1 , and $\text{beta}(0.5, 0.5)$ for ρ . δ and γ are the subject-specific and site-specific random effects, respectively. We assume random subject effects are independent and identically distributed as $\delta \sim N(0, \sigma_{\text{subj}}^2)$ and random site effects are independent and identically distributed as $\gamma \sim N(0, \sigma_{\text{site}}^2)$. For the variances of random subject and site effects, an independent non-informative conjugate prior $\text{inverse-gamma}(0.001, 0.001)$ will be used. The Metropolis sampler algorithm as implemented in the SAS/STAT MCMC Procedure (SAS Institute Inc., 2015)³⁶ will be used to estimate the posterior distributions of the parameters (β_0 , β_1 , ρ). Inferences will be made based on a posterior credible interval for the relevant parameters.

Hypothesis Testing

The null and alternative hypotheses for testing non-inferiority of Test relative to Control are as follows:

$$\begin{aligned} H_0: p_T - p_C \leq -0.1 \\ H_1: p_T - p_C > -0.1, \end{aligned}$$

where p_T and p_C are the probability of success (i.e., acceptable lens fitting) for Test lens and Control lens, respectively. Non-inferiority will be declared if the posterior probability $p(p_T - p_C > -0.1 | \text{data}) \geq .975$.

In the case of all eyes have an acceptable lens fit (i.e., zero unacceptable lens fit), a Bayesian hierarchical model accounting for zero event problem will be considered (Chen & McGee, 2008).³⁷ Details of this model will be provided in the stand-alone SAP.

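### The site-variance prior in 14.6 is not non-informative with 4–6 sites, and p_T and p_C are undefined, so one unacceptable Test eye of 112 can fail the lens-fit test

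*Combined protocol and SAP*

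**What the plan says.** Section 14.6 models the number of acceptable eyes per child and lens with a correlated-binomial mixture. The logit of p contains an intercept, a lens effect, and normal subject and site effects. On the variance priors it states: "For the variances of random subject and site effects, an independent non-informative conjugate prior", namely inverse-gamma(0.001, 0.001). The intercept and lens effect have N(0, 1000) priors, and the between-eye correlation has beta(0.5, 0.5).

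The decision rule is a posterior threshold: "Non-inferiority will be declared if the posterior probability" that p_T − p_C exceeds −0.1 is at least 0.975. The section calls p_T and p_C the success probabilities for the two lenses. It does not say whether they are taken at random effects of zero or averaged over them.

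A different model is foreseen only for one data pattern: "In the case of all eyes have an acceptable lens fit (i.e., zero unacceptable lens fit"). No prior-sensitivity analysis is described.

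Section 14.2 expects few failures ("Given the rare event binary outcome of fit acceptance (i.e., the number of unacceptable fit is very small")) and plans on a "reference (Control lens) rate of 95% (worse-case scenario) for lens fit acceptance". Section 4.3 foresees "Approximately 4 – 6 clinical sites in the United States". Section 2.3 requires both the primary and the secondary hypothesis to be met.

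**The concern.** A variance prior that is nearly flat on the log scale does little harm when many groups and many events inform the variance. Here there are 4–6 sites, and the historical study cited in 14.2 had no unacceptable fits. A single unacceptable eye takes the trial out of the zero-event provision and into the main model. If the prior then settles the answer, a near-perfect result can fail. Because 2.3 makes this test necessary for success, it would take the trial down with it.

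The undefined p_T and p_C add a second problem. With large random-effect SDs, a success probability at random effects of zero is not the acceptance rate that the 10-point margin refers to.

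**Working it through.** **Inputs.** 56 completers, so 112 eyes per lens (14.2); 4–6 sites (4.3); margin −10 points; pass at posterior probability ≥ 0.975; 95% acceptance on both lenses; correlation 0.80 between eyes and 0.50 across periods (14.2); priors as in 14.6, with N(0, 1000) read as variance 1000. Simulations assume equal site sizes, no true site effect and a Gaussian copula for the correlated binary data. Ranges below are over separate runs.

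**1. Table 7's 81%.** The variance of one eye is 0.95 × 0.05 = 0.0475. Ignoring the cross-period correlation, the variance of a child's lens difference is 2 × 0.0475 × 0.9 = 0.0855, so the SE is √(0.0855/56) = 0.0391. The true variance is 2 × (0.0475 × 0.9 − 0.5 × 0.0475) = 0.038, so the true SE is √(0.038/56) = 0.0260. Power = Φ((0.10 − 1.96 × 0.0391)/0.0260) = 81.6%. Simulating 2,000 trials with the correlated beta-binomial **without** random effects gives 80.1%. The full 14.6 model with its stated priors, at 5 sites and 300 trials, gives 88% (averaged over both effects), 94% (averaged over subjects at the trial's own sites) or 96% (effects at zero). Table 7 therefore does not describe the planned analysis.

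**2. Why the site prior matters.** On the scale of log variance, the inverse-gamma(0.001, 0.001) density is proportional to v^(−0.001) once v is well above 0.001. From v = 1 to v = 10⁶ it falls only by the factor 10^(−0.006) = 0.986. The likelihood does not stop it either. If every fit is acceptable and the intercept is held fixed, then as the site SD grows the likelihood tends to the chance that all site effects are positive: 1/16, 1/32 or 1/64 for 4, 5 or 6 sites.

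As an illustration, take one failed Test eye and 5 sites, where the posterior means are about 28 for the intercept and −16 for the lens effect. With a site SD of 10, the share of hypothetical sites where Test fails and Control does not is about Φ(−12/10) − Φ(−28/10) = 0.115 − 0.003 = 0.112. That already exceeds the 10-point margin, and it comes from sites far outside the data.

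**3. One unacceptable Test eye, no Control failure** (observed difference 1/112 = 0.9 points). Posterior probability that p_T − p_C > −0.1:

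| Prior and definition of p | 4 sites | 5 sites | 6 sites |
|---|---|---|---|
| Plan's priors, averaged over subject and site | 0.90 | 0.92–0.93 | 0.93–0.94 |
| Plan's priors, effects at zero | 0.971–0.972 | 0.984 | 0.990 |
| Plan's priors, averaged over subjects at own sites | ≥ 0.9995 | ≥ 0.9995 | ≥ 0.9995 |
| Half-normal(0,1) on both SDs, averaged | 0.992–0.994 | 0.995–0.996 | 0.997 |
| Half-normal(0,1) on site SD only, averaged | 0.994 | 0.997 | not run |

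Without random effects the figure is 0.9998 (5 sites).

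**4. Which variance prior is responsible.** On the averaged definition, inverse-gamma on the subject variance with no site effect gives 0.9996 (4 sites). Inverse-gamma on the site variance with no subject effect gives 0.88 (4 sites) and 0.91 (5 sites). The site prior causes the failure.

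**5. Pass rate when Test is 85% and Control 95%** (nominal 2.5%; 5 sites unless stated):

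| Definition | Plan's priors | Half-normal(0,1) | Half-normal(2.5) |
|---|---|---|---|
| Effects at zero | 68–70%; 66% at 4 sites | 11–13% | 46% |
| Averaged over subject and site | 3.3% (400 trials), 6.0% (480); 4.5% at 4 sites (200) | 1.3–1.7% | 1.3% |

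The first row follows from the scale. The logit at zero random effects is approximately Φ⁻¹(rate) × √(1.7² + SD²). With a subject SD of 3.9 the root is 4.25, giving 1.645 × 4.25 = 7.0 for 95% and 1.036 × 4.25 = 4.4 for 85%. The probabilities are 0.999 and 0.988. A 10-point deficit in acceptance becomes about 1 point.

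**6. Limits on a replacement prior.** In this model the periods are linked only through the random effects. With no site effect, a correlation of 0.50 at 95% acceptance needs a subject SD of about 3.9 logits; SD 1 gives 0.06 and SD 2 gives 0.23. Half-normal(0,1) puts only 2 × (1 − Φ(3.9)) ≈ 0.0001 of its mass above 3.9, so it does not suit the subject SD. For the site SD, the scale still matters: half-normal(2.5) gives about 0.95–0.97 in the one-eye case at 4 and 5 sites, and half-Cauchy(1) on both SDs gives 0.963 at 5 sites.

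**The case against.** The strongest reply is that the harm depends on a definition the plan has not given. With effects at zero, the one-eye case passes at 5 and 6 sites; at the trial's own sites it passes throughout. Section 14 also calls itself an outline and defers detail to a stand-alone SAP, which is not among the documents and may settle the definition. This stands as far as it goes. But 14.6 already fixes the prior, and the reading that rescues the one-eye case by setting effects to zero is the one that passes an 85% lens about 70% of the time.

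It is also fair to say that half-normal(0,1) is itself a choice and that a wider scale still fails. That argues for a sensitivity analysis, not for leaving the present prior unexamined.

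A reader might infer four stronger things that the documents and calculations do not support:
- *The damage is the same however p_T and p_C are computed.* The tables show otherwise.
- *The subject-variance prior causes the one-eye failure.* On its own it gives 0.9996.
- *Type I error on the averaged definition is clearly inflated.* One set of runs gave 6.0%, but another gave 3.3%, about one standard error (0.8 points) above 2.5%.
- *Power falls as acceptance rises, so 95% is not the worst case.* One set of 240 trials per rate gave 92%, 83% and 81% at 95%, 98% and 99%. This was not confirmed, the last step is within noise, and all three exceed the 80% target.

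**Conclusion.** The concern holds in a limited form. The inverse-gamma prior on the site variance is not non-informative for these data. On the averaged definition it turns a 0.9-point observed deficit into a failed 10-point non-inferiority test at 4, 5 and 6 sites (0.90–0.94); with effects at zero it does so only at 4 sites (about 0.97). The zero-event provision does not cover this case. Separately, taking p_T and p_C at zero random effects would let a truly inferior lens pass about 70% of the time, and no prior tried with the random effects kept brings that near 2.5%.

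The figures rest on 56 children (the safety population used in 14.6 may be larger), equal site sizes and no true site effect. They also depend on the wide normal priors for the intercept and lens effect: with SD 2.5 on those instead, the averaged one-eye probability at 5 sites is 0.984. Simulated pass rates carry a Monte Carlo error of about 1–3 points.

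**What to change.** Before database lock, in 14.6 and the stand-alone SAP:

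1. Define p_T and p_C as averaged over the subject and site effects.
2. Replace the inverse-gamma prior on the site variance by a weakly informative prior on the site SD, such as half-normal(0,1) on the logit scale. Keep the subject-SD prior wide enough to allow about 4 logits, so that the 0.50 cross-period correlation in 14.2 remains possible.
3. Pre-specify a sensitivity analysis to the scale of the site-SD prior, including 2.5, and say how a changed verdict will be reported.
4. Re-run power and type I error with the full 14.6 model at 95%, 98% and 99% acceptance, restate Table 7, and check there whether 95% is the least favourable rate.

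The cost is protocol or SAP text and simulation time; no participants or procedures change. The downside is that the site prior becomes mildly informative, with about 95% of its mass below 2 logits, and needs a written justification. In one set of runs, half-normal(0,1) on both SDs lowered simulated power at 95% from about 92% to 83%, still above the 80% target; the site-only change should be simulated in its own right.

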14.7. Other Analyses

Summary statistical analysis will be provided for the following other observations:

Other endpoints:

- Monocular distance (4 m) logMAR visual acuity under dim lighting conditions with a low luminance, high contrast chart (dim LLHC), measured per [REDACTED]
[REDACTED]
- Monocular distance (4 m) logMAR visual acuity under bright lighting conditions with a high luminance, low contrast chart (bright HLLC), measured per [REDACTED]
[REDACTED]

Clinical Study Protocol

Johnson & Johnson Vision Care, Inc.

- Lens centration and movement characteristics, measured per [REDACTED]
- Slit lamp findings, measured per [REDACTED]
- Subject reported ocular symptoms, measured per [REDACTED]
- Pupil diameter (mm)

Further exploratory analysis will be considered if necessary, at discretion of the Study Responsible Clinician.

14.8. Interim Analysis

There will not be an interim analysis performed on this study.

14.9. Procedure for Handling Missing Data and Drop-Outs

Missing or spurious values will not be imputed. The count of missing values will be included in the summary tables and listings.

14.10. Procedure for Reporting Deviations from Statistical Plan

The analysis will be conducted according to that specified in above sections. There are no known reasons for which it is planned to deviate from these analysis methods. If for any reason a change is made, the change will be documented in the study report along with a justification for the change.

15. DATA HANDLING AND RECORD KEEPING/ARCHIVING

15.1. Electronic Case Report Form/Data Collection

The data for this study will be captured on electronic case report forms (eCRFs) using an EDC system (Bioclinica). An authorized data originator will enter study data into the eCRFs using the EDC system. Data collected on equipment that is not captured in EDC will be formatted to the specification of the JJVC database manager and sent to JJVC for analysis.

External Data Sources for this study include: Not applicable.

The clinical data will be recorded on dedicated eCRFs specifically designed to match the study procedures for each visit. Only specifically delegated staff can enter data into the eCRF. Once completed, the eCRFs will be reviewed for accuracy and completeness and signed by the Investigator. The sponsor or sponsor's representatives will be authorized to gain access to the subject record for the purposes of monitoring and auditing the study.

Edit checks, electronic queries, and audit trails are built into the system to ensure accurate and complete data collection. Data will be transmitted from the clinical site to a secure central database as forms are completed or updated, ensuring information accuracy, security, and confidentiality. After the final database lock, the Investigator will be provided with Individual

Clinical Study Protocol

Johnson & Johnson Vision Care, Inc.

Patient Profiles (IPP) including the full audit trail on electronic media in PDF format for all of the study data. The IPP must be retained in the study files as a certified copy of the source data for the study.

The content and structure of the eCRFs are compliant with ISO14155:2011.¹

15.2. Subject Record

At a minimum, subject record should be available for the following:

- subject identification
- eligibility
- study identification
- study discussion
- provision of and date of informed consent
- visit dates
- results of safety and efficacy parameters as required by the protocol
- a record of all adverse events
- follow-up of adverse events
- medical history and concomitant medication
- test article receipt/dispensing/return records
- date of study completion
- reason for early discontinuation of test article or withdrawal from the study, if applicable

The subject record is the eCRF or an external record. The author of an entry in the subject record must be identifiable. The first point of entry is considered to be the source record.

Adverse event notes must be reviewed and initialed by the Investigator.

15.3. ClinicalTrials.gov

The study will be registered on clinicaltrial.gov by the Sponsor.

16. DATA MANAGEMENT

16.1. Access to Source Data/Document

The Investigator/Institution will permit trial-related monitoring, audits, IEC/IRB review and regulatory inspection(s) by providing direct access to source data/documents. Should the clinical site be contacted for an audit by an IEC/IRB or regulatory authority, JJVC must be contacted and notified in writing within 24 hours.

16.2. Confidentiality of Information

Information concerning the investigational product and patent application processes, scientific data or other pertinent information is confidential and remains the property of JJVC. The

Clinical Study Protocol

Johnson & Johnson Vision Care, Inc.

Investigator may use this information for the purposes of the study only. It is understood by the Investigator that JJVC will use information developed in this clinical study in connection with the development of the investigational product and therefore may disclose it as required to other clinical investigators and to regulatory agencies. In order to allow the use of the information derived from this clinical study, the Investigator understands that he/she has an obligation to provide complete test results and all data developed during this study to the Sponsor.

16.3. Data Quality Assurance

Steps will be taken to ensure the accuracy and reliability of data, include the selection of qualified investigators and appropriate clinical sites and review of protocol procedures with the Principal Investigator. The Principal Investigator, in turn, must ensure that all Sub-Investigators and clinical site personnel are familiar with the protocol and all study-specific procedures and have appropriate knowledge of the study article.

Training on case report form completion will be provided to clinical site personnel before the start of the study. The Sponsor will review case report forms for accuracy and completeness remotely during the conduct of the study, during monitoring visits, and after transmission to data management. Any data discrepancies will be resolved with the Investigator or designee, as appropriate.

Quality Assurance representatives from JJVC may visit clinical sites to review data produced during the study and to assess compliance with applicable regulations pertaining to the conduct of clinical trials. The clinical sites will provide direct access to study-related source data/documents and reports for the purpose of monitoring and auditing by JJVC and for inspection by local and regulatory authorities.

16.4. Data Monitoring Committee (DMC)

Not applicable.

17. CLINICAL MONITORING

The study monitors will maintain close contact with the Principal Investigator and the Investigator's designated clinical site personnel. The monitor's responsibilities will include:

- Ensuring that the investigation is being conducted according to the protocol, any subsequent versions, and regulatory requirements are maintained.
- Ensuring the rights and wellbeing of subjects are protected.
- Ensuring adequate resources, including facilities, laboratories, equipment, and qualified clinical site personnel.
- Ensuring that protocol deviations are documented with corrective action plans, as applicable.
- Ensuring that the clinical site has sufficient test article and supplies.
- Clarifying questions regarding the study.

Clinical Study Protocol

Johnson & Johnson Vision Care, Inc.

- Resolving study issues or problems that may arise.
- Reviewing of study records and source documentation verification in accordance with the monitoring plan.

